# Safety outcome

1. Rate of procedure complications including respiratory failure, pneumothorax, anesthetic complications, and bronchopulmonary hemorrhage

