# **Outcomes Definitions**

- *Rate of complications:* Number of procedures resulting in any complication divided by the total number of procedures.
- *Rate of specific complication:* Number of procedures resulting in a specific complication divided by the total number of procedures.
- *Need for additional diagnostic procedures:* Any diagnostic procedure performed after the study bronchoscopy which targets the same peripheral lesion (including repeat bronchoscopy, transthoracic needle biopsy, or surgical lung biopsy) will be considered an additional diagnostic procedure. Repeat biopsies of lesions determined to be malignant by study bronchoscopy which are 1) performed specifically to obtain additional tissue for further testing but that does not change the malignant diagnostic, or 2) therapeutic surgical resection of such lesions, will not be considered additional diagnostic procedures.
- *Radiation exposure:* Radiation dose delivered to the patient during the study bronchoscopy, recorded as a dose area product (mGy/cm2).
- *Diagnostic accuracy:* Number of true positive (malignant) lesions plus true negative (specific benign diagnosis) lesions with no evidence of malignancy at 12-month follow-up (no interval biopsy diagnostic of malignancy, regression on CT or stable size with no plan for repeat diagnostic procedure), divided by the total number of biopsied lesions.

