## **Reporting Period**

Procedural related risks are described in detail below. For example, adverse events such as pneumothorax and bronchopulmonary hemorrhage may result in the need for a chest tube or blood transfusion, respectively. These clinical adverse events are recorded within the case report form (CRF) and are known potential complications of the usual care procedures. As such, these events will not be reported to the IRB as an adverse event related to the research and instead will be collected as events for the purposes of the DSMB. All serious unanticipated adverse events will be reported to the DSMB and IRB per current institutional standards. These may include events resulting in escalation of care such as the need to remain in the hospital following the bronchoscopy procedure. As these procedures are standard of care for sampling PPLs, collection of data regarding adverse events and serious adverse events will be limited in this study:

- Any serious or non-serious adverse event related to research procedures (i.e., the consent process, HIPAA compliance, etc.) will be collected.
- Any serious adverse event that occurs  $\leq 7$  days after the procedure.
- A written report will be sent to the DSMB and IRB within 15 calendar days of the PI being notified.

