## **Procedure Related Risks**

The procedures being studied are considered standard of care and are being undertaken for routine care of the patient. As such, we do not expect that enrollment in this study will result in an increased risk for the patient above what they are experiencing as part of their routine care. The risks of navigational bronchoscopy for the biopsy of PPLs are well defined, and include pneumothorax, bronchopulmonary hemorrhage, which could result in the need for a blood transfusion, respiratory failure, and anesthetic complications. Risk of death is estimated around 1/10,000. Pneumothorax is the most common complication, occurring in approximately 2% of cases in a large prospective multicenter study (3) and may result in the need for a chest tube. Existing data for SSCB indicates a similar risk profile, which also underlie its recent FDA clearance via 510(k) pathway which requires a demonstration of similar risk to a predicate approved or cleared device. Procedural risks are collected in the CRF and may be reviewed by the DSMB. As these are considered procedural risks and not research related risks, they will not be reported to the IRB.

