Biopsies obtained without the use of EMN or SSCB (e.g., sampling of central lymph nodes using the linear endobronchial ultrasound bronchoscope) will not be included in the diagnostic yield calculations. In case of repeat bronchoscopies, only the index bronchoscopy will be included in the diagnostic yield calculation.

Secondary Outcomes

There is one secondary outcome for the trial, which will be collected during the bronchoscopy procedure.

a) Duration of procedure (in minutes), defined as time from the start of airway registration to

the removal of the bronchoscope after completion of navigation procedures.

Exploratory Endpoint(s)

There are three exploratory endpoints that are prespecified. These can be collected during and immediately after the bronchoscopy procedure, and/or during the follow-up period.

a) Need for additional diagnostic procedures. Any diagnostic procedure performed within 12 months of the study bronchoscopy that targets the same peripheral lesion (including repeat bronchoscopy, transthoracic needle biopsy, or surgical lung biopsy) will be considered an additional diagnostic procedure.

1. Repeat biopsies of lesions determined to be malignant by study bronchoscopy which are 1) performed specifically to obtain additional tissue for further testing but that does not change the malignant diagnosis, or 2) therapeutic surgical resection of such lesions, will not be considered additional diagnostic procedures.

b) Radiation exposure, defined as radiation dose delivered to the patient during the study bronchoscopy, recorded as a dose area product (mGy/cm2).

Diagnostic accuracy

Diagnostic accuracy will be assessed for the two devices. Lesions will be categorized as positive (malignant) lesions or negative (specific benign diagnosis). The criterion standard for a negative diagnosis will be no evidence of malignancy at 12-month follow-up (no interval biopsy diagnostic of malignancy, regression on CT or stable size with no plan for repeat diagnostic procedure).

Safety outcome

The main safety outcome for this trial is occurrence of procedure complication(s), defined as the occurrence of any of the following: respiratory failure, pneumothorax, anesthetic complications, and bronchopulmonary hemorrhage.

Safety outcomes will be reported overall and by type.

Statistical analysis plan for **R**obotic versus Electromagnetic Bronchoscopy for Pulmonary LesIon Assessme**NT**: the RELIANT trial PI: [name]

Analysis dataset

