The primary analysis for the trial will use an intent-to-treat approach. Participants will be evaluated by treatment group as assigned regardless of what was delivered. All eligible participants will be included.

The primary outcome variable (diagnostic yield) will be compared between groups using a generalized linear mixed model with one-sided test. The primary model will be covariate adjusted, including fixed effects for device assignment, lesion size, density, peripheral location, and bronchus sign, and a random effect for operator. Should the model demonstrate signs of overfitting, covariates may be selected based on priority order (device assignment, lesion size, density, peripheral location, sign, operator).

If non-inferiority is demonstrated, we will proceed with a superiority analysis using the same approach as the non-inferiority analysis, an adjusted generalized linear mixed effects model with the same covariates used in the primary analysis. No adjustment will be made for multiplicity. The superiority analysis would be conducted at a one sided p-value of 0.05.

Secondary and exploratory analysis

A sensitivity analysis using a *per protocol* approach will be conducted to analyze participants based on the device used. We will use the same approach as the primary analysis, an adjusted generalized linear mixed effects model using the same covariates.

The secondary outcome, procedure duration, will be compared between study groups using a linear mixed model. If the procedure duration is skewed, alternative models may be pursued,

Statistical analysis plan for **R**obotic versus Electromagnetic Bronchoscopy for Pulmonary LesIon AssessmeNT: the RELIANT trial PI: [name] such as a cox regression. The primary model will be covariate adjusted following a similar approach to the analysis of the primary outcome. Analysis of the exploratory endpoints will follow a similar approach.

Safety analysis

Procedure complications are expected in usual care, although uncommon. We will report all procedure complications for each device, overall and by type. If event rates exceed 5%, we may proceed with a comparative analysis, which will involve a generalized linear mixed regression model for binary outcomes as specified for the main analysis, with the exception that covariate adjustment may not be possible. The safety analysis dataset will group participants by device used, regardless of assignment.

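### The SAP narrows the protocol's open safety outcome (any procedure complication) to a closed list of four types, and plans no by-device summary of the serious adverse events collected to day 7.

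*SAP*

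**What the plan says.** **Protocol.** The synopsis and the Safety outcome section both use an open list: "Rate of procedure complications including respiratory failure, pneumothorax, anesthetic complications, and bronchopulmonary hemorrhage". Outcomes Definitions sets the numerator and denominator of the overall rate: "Number of procedures resulting in any complication divided by the total number of procedures". Comparing complication rates between the platforms is a stated aim in the Objectives section.

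Under Reporting Period, the protocol also collects "Any serious adverse event that occurs" within 7 days of the procedure, whatever its type. The study calendar schedules adverse events on Day 1 and within 7 days. The same section says of serious unanticipated events, which go to the DSMB and IRB: "These may include events resulting in escalation of care such as the need to remain in the hospital following the bronchoscopy procedure".

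**SAP.** Under Outcomes, Safety outcome, the main safety outcome is the occurrence of procedure complications, "defined as the occurrence of any of the following: respiratory failure, pneumothorax, anesthetic complications, and bronchopulmonary hemorrhage". Under Safety analysis: "We will report all procedure complications for each device, overall and by type". A regression comparison may follow if event rates exceed 5%. The safety dataset groups participants by device used. The SAP defines no other safety outcome and does not mention serious adverse events, deaths or hospital admissions.

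**The concern.** The trial has one safety outcome, and its two governing documents give that outcome different numerators. The protocol's list is illustrative and the SAP's is exhaustive. The SAP gives no reason for the narrowing, and its revision log describes the changes to the safety outcome only as minor clarifications.

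An analyst who follows the SAP definition will report a complication rate that can be lower than the protocol's and can never be higher. Any difference between platforms in complications outside the four types would not show in that rate. The serious adverse events to day 7 are collected but have no planned place in the by-device report. The results are meant to inform which platform a hospital buys, so the safety summary should have one agreed meaning before the data are seen.

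**Working it through.** The documents give no sample size, precision or expected rate for the safety outcome, so there is no safety figure to reproduce. The power calculation concerns diagnostic yield and is not affected. The check sets the definitions side by side and then asks how likely the SAP's modelled comparison is to be run.

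**1. How each kind of event is treated**

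| Event | Protocol complication rate | SAP main safety outcome | By-device summary planned in SAP |
|---|---|---|---|
| Procedure complication of a listed type | Counted | Counted | Yes |
| Procedure complication of another type, not serious | Counted (any complication) | Not counted | Unclear: depends on how Safety analysis is read |
| Procedure complication of another type, serious, by day 7 | Counted | Not counted | Unclear as a complication; none as a serious adverse event |
| Serious adverse event by day 7 not caused by the procedure | Not counted: no passage makes it a procedure complication | Not counted | None |

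Rows 2 and 3 are the conflict between the protocol and the SAP. Row 4 is not a conflict in the complication rate. It is a set of collected data with no planned summary.

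**2. The conflict inside the SAP**

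The Safety analysis sentence can be read in two ways. If procedure complications there carries the meaning just given under Safety outcome, the report covers four types only and departs from the protocol. If it means every complication, it departs from the SAP's own definition. Either reading needs reconciling.

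**3. How likely is the modelled comparison?**

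Inputs: 202 per arm, so N = 2 × 202 = 404, or the enrolment target N = 425 (sample size sections of both documents); the 5% condition (SAP, Safety analysis); pneumothorax in about 2% of cases, described as the most common complication (Protocol, Procedure Related Risks).

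Assumptions: the 5% condition is applied to the pooled rate, and events are independent. The documents give no overall complication rate, so a range is shown.

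Threshold: 0.05 × 404 = 20.2, so at least 21 events are needed; 0.05 × 425 = 21.25, so at least 22.

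Formula: P(X ≥ threshold), with X binomial (N, p).

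| True rate p | Expected events (N = 404 / 425) | P(rate exceeds 5%) (N = 404 / 425) |
|---|---|---|
| 2% | 8.1 / 8.5 | 0.009% / 0.006% |
| 3% | 12.1 / 12.8 | 1.2% / 1.0% |
| 4% | 16.2 / 17.0 | 13.6% / 13.4% |
| 5% | 20.2 / 21.3 | 45.9% / 46.5% |

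Up to a true rate of 5%, the condition is more likely missed than met, and even when it is met the SAP says only that a comparison may follow. The descriptive report is therefore probably the only safety comparison.

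**4. Deaths**

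The protocol states: "Risk of death is estimated around 1/10,000". Expected deaths are 425 × 0.0001 = 0.04, and the chance of at least one is 1 − (1 − 0.0001)^425 = 4.2% (4.0% at N = 404).

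**The case against.** A reader might infer that a death, stroke, infection or unplanned admission outside the list can never appear in the comparison of devices, and that such a patient is recorded as complication-free. The documents do not support that, for five reasons.

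- The Safety analysis section promises all procedure complications for each device, and the SAP calls the four-type composite only the main safety outcome. The texts conflict; they do not clearly exclude.
- Neither document defines anesthetic complications or respiratory failure. All procedures are done under general anesthesia, so some periprocedural events could be coded to one of these types.
- A serious adverse event is not the same as a procedure complication. The protocol collects serious events within 7 days without requiring a link to the procedure, and no passage makes each one a complication. The hospital-stay example illustrates serious unanticipated events reported to the DSMB and IRB, not the complication outcome.
- Serious events are not lost to oversight. The DSMB is asked to evaluate them, and a written report goes to the DSMB and IRB within 15 calendar days.
- There may be no modelled comparison from which to be excluded, as shown above.

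All five stand as limits on the point. They do not remove it. DSMB review monitors the trial but does not settle what is reported by device at the end. Undefined categories leave the handling of an unlisted event to judgment in an open-label trial, and the blinded panel is assigned to biopsies, not complications. An optional comparison makes the content of the descriptive table matter more.

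**Conclusion.** The point holds as a discrepancy between documents and a gap in reporting. The SAP's definition is narrower than the protocol's and is inconsistent with its own reporting promise. The SAP plans no by-device summary of the serious adverse events to day 7. It should be corrected.

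No magnitude can be claimed, because the documents give no rate for procedure complications outside the four types or for serious adverse events generally. The one stated rate for a severe event, death, implies about 0.04 expected deaths, so the plan's own figures do not suggest that deaths would go missing in any number. It would also go too far to say that either platform's safety would be misjudged.

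The statement that the descriptive report is probably the only safety comparison assumes a pooled reading of the 5% condition, independent events and a true overall rate no higher than about 5%. The SAP calls complications uncommon, but the overall rate is not stated. The primary analysis and sample size are unaffected.

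**What to change.** In the SAP:

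1. Under Safety outcome, restore the protocol's definition: any procedure complication, including the four named types, with a further category for other procedure complications. Use the same term in the same sense under Safety analysis, so that the overall figure and the breakdown by type rest on one definition.
2. Under Safety analysis, add a separate descriptive table of all serious adverse events and deaths to day 7, by device used. This matches the grouping already chosen for the safety dataset.
3. Keep the two apart. Adding all-cause serious adverse events to the complication rate would put events into the numerator that the protocol does not place there, and would create a new mismatch.

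The cost is a change of SAP wording and one extra table from data the protocol already collects. The reported complication rate may be slightly higher than under the four-type definition.

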# **Study Population**

#### Inclusion Criteria:

- 1.  $\geq$  18 years of age at time of bronchoscopy.
- 2. Undergoing navigational bronchoscopy for biopsy of PPL

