# Secondary outcomes

1. Duration of procedure (in minutes), defined as time from the start of airway registration to the removal of the bronchoscope after completion of navigation procedures.

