#### **Study Procedures**

Written research informed consent for the collection of data will be integrated within the clinical workflow when obtaining procedural consent (refer to Informed Consent section below) and all eligible patients will be enrolled. An allocation envelope will be opened by OR staff each morning to determine which room each platform will be set up in. The pre-operative steps and procedure will proceed per usual standard of care. Intubation and ventilation will follow our standard clinical protocol which is identical for both platforms (8.5 mm size endotracheal tube, a recruitment maneuver once the endotracheal tube is secured (PEEP of 40 cmH20 for 40 seconds), followed by ventilation with a PEEP of 15 cmH20 with as minimal FiO2 needed to maintain a SpO2 of >90%). The navigation procedures will be planned using pre-procedure CT scans of the chest and the planning software specific to each platform.

Bronchoscopy will be performed by interventional pulmonologists with expertise in navigational bronchoscopy and as per standard of care. Procedures will be performed under general anesthesia with neuromuscular blockade. Radial endobronchial ultrasound will be available for all procedures. Biopsies will be obtained using transbronchial needles, biopsy forceps, cytology brushes, cryoprobes, and/or other sampling devices at the discretion of the

bronchoscopist. Rapid on-site evaluation will be performed to assess for specimen adequacy. Additional biopsies obtained without the use of guided bronchoscopy (e.g., sampling of central lymph nodes using the linear endobronchial ultrasound bronchoscope) will be collected if clinically indicated but will be excluded from PPL diagnostic yield calculations. The procedure will be deemed non-diagnostic if the proceduralist is unable to reach the nodule (no biopsies obtained, representing navigation failure) or if a complication occurs before biopsies are obtained. All patients will recover based on our usual standard of care, which includes two hours of monitoring in the PACU before being discharged.

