#### **REGULATORY CONSIDERATIONS**

## **Informed Consent**

We propose a pragmatic, open-label, cluster-randomized trial to compare the diagnostic yield of these standard of care bronchoscopic platforms (EMN vs. SSCB). We will randomly allocate which system (EMN or SSCB) is set-up in each operating room on a given day, and all

peripheral pulmonary lesion biopsies occurring in that room on that day will be performed with the assigned system.

We currently perform advanced diagnostic bronchoscopy in two operating rooms within the main VUMC ORs. We have one EMN system and one SSCB system. Both systems require time to set up, including moving equipment into and out the OR and running calibration steps. OR staff typically arrives one hour before procedures are scheduled to begin each day to set up. Each OR hosts 5-8 bronchoscopies daily, up to four of which on a given day may be EMN/SSCB cases (often back-to-back with each other). Additionally, these procedures need to be planned by the bronchoscopist ahead of time. To accommodate traditional individual patient-level randomization would require moving these platforms between ORs multiple times daily and planning the procedure after consent and enrollment. This would result in a tremendous disruption of our workflow, procedural delay, and suboptimal patient care rendering this study impracticable. Furthermore, about 20% of navigational bronchoscopy cases are performed only after intrathoracic lymph nodes are sampled and negative for malignancy (per rapid on-site cytological examination). Patients with evidence of cancer in their lymph nodes would no longer have an indication for navigational bronchoscopy and would then be excluded after randomization if we were to use traditional individual patient-level randomization, which would significantly impact accrual and power.

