Patients who are undergoing a navigational bronchoscopy for biopsy of a peripheral lung lesion and are ≥ 18 years of age at the time of the procedure will be included in this study. Patients will be excluded if they are enrolled in a different study requiring use of one of these specific platforms or if they decline to participate.

Study Design:

This is a single center, open label, pragmatic, non-inferiority, cluster randomized controlled trial comparing clinical outcomes between patients assigned to receive a diagnostic bronchoscopy with either the IonTM Endoluminal System (SSCB) or the ILLUMISITETM Platform (EMN) platform.

Randomization:

Operating rooms are set up each morning with one of the two devices for the day's of prescheduled procedures. Cluster randomization will be used for this study given impracticability of patient-level 1:1 parallel randomization in these circumstances. The ILLUMISITETM Platform (EMN) and IonTM Endoluminal System (SSCB) will be randomly allocated to our two operating rooms each day. All patients undergoing a navigational bronchoscopy will have their procedure performed with the platform assigned to their operating room for the day. A biostatistician not involved in patient care will generate the randomization sequence. Random permuted blocks may be used to ensure balanced cluster allocation. A bronchoscopy scheduler with no knowledge of the allocation scheme will schedule each patient into one of the two operating rooms. Allocations will be concealed in sealed envelopes which will be opened every morning by the operating room staff preparing the rooms.

Sample Size Considerations:

The study team performs 1-4 guided bronchoscopies per day (average of 2 per day) and approximately 400 per year. Based on data from prior studies and the study team's published data, we estimated the diagnostic yield of EMN to be 80%. The diagnostic yield of SSCB has not been fully elucidated, but published data suggest an overall diagnostic yield of 80% as well. Assuming the diagnostic yield for the ILLUMISITE[™] Platform (EMN) is 80%, with a non-

Statistical analysis plan for Robotic versus Electromagnetic Bronchoscopy for Pulmonary LesIon AssessmeNT: the RELIANT trial

PI: [name]

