inferiority margin set at 10%, cluster size of 2, and no intracluster correlation, we need 202 clusters (operating days) to have an 80% power to conclude noninferiority at a one-sided type I error rate of 5%, which corresponds to a target of 425 subjects to reach 202 per arm. The noninferiority margin has been chosen based on what would be considered a clinically significant difference (or, put differently, a difference which might influence a hospital to purchase one platform over the other). In case our average cluster size does not reach 2, we will plan to increase the number of clusters to meet our target enrollment of 425 subjects to reach 202 per arm.

Interventions

All patients meeting the eligibility criteria for this study will be enrolled. Cluster randomization will be used, and patients will be assigned to one of the two comparator arms:

a) IonTM Endoluminal System (SSCB)

b) ILLUMISITE[™] Platform (EMN)

Outcomes

Primary Outcome

The primary endpoint will be diagnostic yield, defined as the proportion of procedures that results in acquisition of lesional tissue.

Lesional tissue is defined by the presence of pathological findings that readily explain the presence of a pulmonary lesion. The following common pathological findings are pre-specified:

- Malignancy
- Specific benign pathologic finding including
 - Organizing pneumonia
 - Frank purulence/robust neutrophilic inflammation
 - o Granulomatous inflammation
 - Other specific benign findings such as hamartoma, amyloidoma or other uncommon causes of PPLs with distinctive pathological patterns.

Biopsies not meeting any of the above lesional pathological criteria will be adjudicated as not meeting the primary outcome (not being "diagnostic"), including biopsies with normal lung parenchyma or airway components on biopsy, atypia not diagnostic of malignancy, or non-specific inflammation. A blinded panel will review all non-malignant biopsies at the end of accrual to confirm specific benign or non-diagnostic findings on biopsy. Procedures will be adjudicated as not meeting the primary outcome if the procedure starts but biopsies are not obtained (due to failure to navigate to the lesion, or complication, or equipment failure). A procedure will be considered started at induction of general anesthesia.

Statistical analysis plan for Robotic versus Electromagnetic Bronchoscopy for Pulmonary LesIon AssessmeNT: the RELIANT trial PI: [name]

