The analysis for the trial will use a intent-to-treat approach. Participants will be evaluated by treatment group as assigned regardless of what was delivered; participants will be excluded if their procedure did not begin, defined as the start of the navigation procedure itself. All eligible participants will be included.

The safety analysis dataset will group participants by device used, regardless of assignment.

Statistical Approach

Our initial analysis will be descriptive in nature, summarizing information that characterizes the cohort and the outcomes. Then, we will proceed with inferential analysis. No interim analyses are planned.

Descriptive Analysis

To characterize the study sample, baseline demographic and clinical data will be described overall and by group. Categorical variables will be described using frequencies and proportions, and continuous variables will be described using means and standard deviations or medians and interquartile ranges, as appropriate. Missingness will be reported for each variable. At a minimum, the following variables will be described at time of enrollment:

- Age (years)
- Gender (male, female, unknown)
- Race (African American, Asian/Pacific Islander, Caucasian, Multiple, Native American, Other, Unknown)
- Ethnicity (Hispanic, Non-Hispanic, Unknown)
- History of cancer (yes/no)
- Smoking History (current, former, never)
- Body mass index (BMI)
- Lesion characteristics
 - o Size (mm)
 - Location (middle vs peripheral)
 - Upper lobe (yes/no)
 - Density (solid, part solid, ground glass opacity)
 - Distance from pleura (cm)
 - Bronchus sign present (yes/no)
- Procedure details

Statistical analysis plan for **R**obotic versus Electromagnetic Bronchoscopy for Pulmonary LesIon AssessmeNT: the RELIANT trial PI: [name]

PI: [name]

- Rapid onsite evaluation (yes/no)
- o Operator
- Digital tomosynthesis (yes/no)
- Cone beam computed tomography (yes/no)
- Biopsy tools

We will describe the outcome variables overall and grouped by study arm using the same approach as for the demographic data. Summary statistics and graphical representations may be displayed, and missingness will be reported for each variable. No statistical comparisons between groups will be done for this descriptive analysis.

Primary analysis

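### The SAP's analysis-set rule drops patients who never reach navigation, although its endpoint rule counts complications and equipment failures from induction onward as non-diagnostic

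*SAP*

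**What the plan says.** Both documents define the primary endpoint in the same words (Protocol, Primary Outcome; SAP, Primary Outcome): "A procedure will be considered started at induction of general anesthesia". A procedure that has started but yields no biopsy is adjudicated as not meeting the endpoint. The listed reasons are unsuccessful navigation, a complication and an equipment failure. Protocol, Study Procedures, likewise calls the procedure non-diagnostic "if a complication occurs before biopsies are obtained".

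SAP, Analysis dataset, adopts an intent-to-treat approach for the trial's analysis and then adds that "participants will be excluded if their procedure did not begin, defined as the start of the navigation procedure itself". SAP, Primary analysis, restates intent-to-treat with "All eligible participants will be included" and does not repeat the exclusion. The protocol has no exclusion tied to the start of navigation.

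Two other passages bear on the point. Procedure duration is "defined as time from the start of airway registration to the removal of the bronchoscope after completion of navigation procedures". Protocol, Informed Consent, says that in about 20% of navigational cases lymph nodes are sampled first and found negative, and adds: "Patients with evidence of cancer in their lymph nodes would no longer have an indication for navigational bronchoscopy".

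**The concern.** Induction and the start of navigation are different moments, separated by intubation, a recruitment maneuver and sometimes node sampling. A patient who has a complication or an equipment failure in that interval is a non-diagnostic procedure under the endpoint definition and is absent under the analysis-set definition. Applying the two rules in sequence does not reconcile them: if the exclusion comes first, the induction sentence has almost nothing left to govern.

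The trial is an open-label non-inferiority comparison of two devices. The exclusion acts after allocation and could remove events that the endpoint was written to count. If the choice is left until results are known, either rule could be defended from the text.

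**Working it through.** **Who is affected**

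| Event | Endpoint rule (induction) | Analysis-set rule (navigation start) |
|---|---|---|
| Complication or equipment failure after induction, before navigation | non-diagnostic | excluded |
| Unsuccessful navigation | non-diagnostic | non-diagnostic |
| Complication or equipment failure during navigation, no biopsy | non-diagnostic | non-diagnostic |
| Navigation not attempted because nodes are positive | started, no navigational biopsy, reason not listed | excluded |

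Only the first and last rows differ. For the last row, the eligibility wording ("Undergoing navigational bronchoscopy for biopsy of PPL" in the protocol, "Patients who are undergoing a navigational bronchoscopy for biopsy of a peripheral lung lesion" in the SAP) may already place these patients outside the trial. Neither document says so, and the SAP scores procedures with a missing primary outcome as not diagnostic.

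**Inputs.** From the protocol's sample size section and its table: EMN yield 0.80, margin 0.10, 202 per arm, one-sided alpha 0.05, no intracluster correlation, Farrington-Manning test. Assumed, because the documents give no rate: a fraction f = 1% or 2% of patients in the affected arm has an event in the first row (202 × 0.01 ≈ 2 patients; 202 × 0.02 ≈ 4).

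**Formula.** Probability of concluding non-inferiority = Φ[(p1 − p2 + 0.10 − 1.645·s0)/s1], with p1 for SSCB and p2 for EMN. Here s0 is the standard error at the restricted estimates under the null, and s1 the standard error at the true yields.

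**The plan's own figure.** At 0.80 in both arms the restricted estimates are 0.7411 and 0.8411, so s0 = 0.04015 and s1 = 0.03980. Then (0.10 − 1.645 × 0.04015)/0.03980 = 0.853 and Φ = 0.8033, which matches the protocol's 0.80327. The table's other row (256 per arm, alpha 0.025) also reproduces, at 0.80275.

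**Type I error under the exclusion, induction rule as target.** The true yields with failures counted are SSCB 0.70 and EMN 0.80, exactly at the margin. Excluding the failures changes an affected arm's yield to (counted yield)/(1 − f) and its size to 202(1 − f).

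Example, SSCB only, f = 1%: the SSCB yield is 0.70/0.99 = 0.7071 and the difference is −0.0929. With s0 = 0.04274 and s1 = 0.04275, (0.0071 − 1.645 × 0.04274)/0.04275 = −1.48, so Φ = 0.0696.

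| Failures | Expected difference, f = 1% / 2% | Type I error, f = 1% / 2% |
|---|---|---|
| SSCB only | −9.3 / −8.6 points | 7.0% / 9.5% |
| Equal in both arms | −10.1 / −10.2 points | 4.8% / 4.5% |
| EMN only | −10.8 / −11.6 points | 3.3% / 2.1% |

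If the navigation-start yields are taken as the target instead (0.70 against 0.80 after exclusion), the test holds 5.0%.

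**Power.** Take a counted yield of 0.80 in both arms. The induction rule gives 80.33%. The navigation-start rule gives 80.98% or 81.71% at equal rates of 1% or 2%, a gap of 0.7 or 1.4 points. With SSCB-only failures it gives 85.67% or 90.06%, a gap of 5.3 or 9.7 points.

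All figures are unadjusted. The effect on the planned covariate-adjusted mixed model was not computed.

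**The case against.** The strongest reply is that the documents already lean one way. The section governing the primary analysis omits the exclusion and includes all eligible participants, and the protocol carries only the endpoint rule. That stands, and a reader who inferred that the two rules have equal support would be going too far. It does not close the matter. The exclusion is written for the trial's analysis as a whole, so it reaches the primary analysis unless something says otherwise, and nothing does.

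The second reply is that few patients can be affected. Platforms are set up and calibrated before the day's cases, and airway management is identical for both. The only complication frequency in the protocol is about 2% for pneumothorax over the whole procedure. This also stands: the rates of 1% and 2%, and their placement in one arm, are illustrations.

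The third is that the exclusion was probably meant for patients whose positive nodes remove the reason to navigate. That purpose would be sensible, but the sentence does not state it, and as worded it also removes early equipment failures and complications.

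The last is that the induction rule has a price. If 80% is the yield among navigated procedures, SSCB-only failures lower the SSCB yield to 0.80 × 0.99 = 0.792 or 0.80 × 0.98 = 0.784, and power under the induction rule to 73.8% or 66.5%. That is correct, but the loss comes from counting real SSCB failures, which the endpoint definition intends.

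**Conclusion.** The contradiction is in the text and affects who belongs to the primary analysis set. It is confined to complications and equipment failures between induction and navigation, plus the unstated status of node-positive patients. It should be fixed, but it does not threaten the design.

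Two stronger inferences are not supported. One is that the SAP discards navigation failures, or device failures generally; those arising once navigation has begun count under both rules. The other is that the trial's type I error is 7% to 9.5%. Those values need assumed failures in the SSCB arm alone and the induction rule as target. They measure disagreement between two definitions and do not show a faulty test. Only an SSCB excess of early failures or complications pushes towards a false non-inferiority conclusion; equal rates or an EMN excess make the test conservative. Without event rates, the actual size and direction are unknown.

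**What to change.** Before unblinding, amend the SAP as follows.

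- In Analysis dataset, replace the navigation-start definition with the induction definition already used for the endpoint, and state in Primary analysis that it applies there.
- State that patients for whom navigation was not attempted because node sampling removed the indication are outside the analysis set, with the reason taken from the on-site cytology record, and that the missing-outcome rule does not apply to them.
- State that procedure duration is analysed only in patients who reached airway registration, since it is timed from there. Otherwise patients induced but never registered would enter the set with no duration and no rule for handling it.
- Report all post-allocation exclusions by arm and reason.
- Run the navigation-start rule as a sensitivity analysis, taking airway registration as the start of navigation.

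The cost is wording and one further model run. Planned power stays at 80.3% if the assumed 80% yield counts failures, as the endpoint does. Relative to the navigation-start rule, the power given up is the 0.7 or 1.4 points (equal rates), or 5.3 or 9.7 points (SSCB only), shown in the working.
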